5.5.1 Bronchoscopy and EBUS procedure

EBUS-FNA of the ipsilateral and contralateral hilar and mediastinal lymph nodes will be performed within 2 weeks before and between weeks 2 and 3 after SBRT. Patient preparation and sedation will be performed according to regular institutional practice. Needle aspirations will be performed with a 22-gauge needle and 15 passages of the needle per lymph node. The ipsilateral hilar and mediastinal TDLNs will be sampled.

5.5.2 Lymph node analysis

Cells obtained through needle aspirations will be collected in 7.5ml of culture medium (Iscove's Modified Dulbecco's Medium (IMDM)). Since these aspirates contain small tissue components, the specimen will be enzymatically digested for 45 minutes at 37°C in a sterile glass flask by adding 30ml of IMDM with 0.02% DNase and 0.1% Collagenase (60). The cell suspension will then be filtered through a 100µm sterile filter and the flask is rinsed with 20ml IMDM. Cells will be pelleted by centrifugation (5 minutes, 530xg) and counted using trypan blue staining to identify dead cells. Depending on the cell yield, the following immune subsets will be analyzed by flow cytometry using subset-specifying markers (in order of

interest): 1). CD4, CD8 and T regulatory cells (FoxP3), 2). MDSC, 3). T-cell activation and memory/effector phenotypes, 4). myeloid DC subsets, 5). plasmacytoid DC, 6). NK/NKT cells, 7). $\gamma\delta$ T cells and 8) B cells.

For flow cytometry, surface marker staining will be performed by incubating the cells with specific antibodies for 30 minutes at 4°C in PBS supplemented with 1% BSA and 0.02% NaN₃ (FACS buffer). If erythrocytes are abundant in the specimen, these will be lysed by adding BD lysis buffer after 15 minutes of surface antibody staining, after which cells will be stained for an additional 15 minutes. Cells will be washed in FACS buffer and if no intracellular markers need to be stained (FoxP3), cells are ready for analysis. For intracellular staining of FoxP3 and CTLA-4, cells will be permeabilized and fixated using the eBioscience FoxP3 fix/perm kit according to manufacturer's guidelines: cells are first incubated with perm/fix solution for 30 minutes at 4°C and washed with perm/wash solution before blocking with normal rabbit serum (for FoxP3 stainings) and addition of FoxP3 or CTLA-4 specific antibodies. Antibody staining is performed for 30 minutes at 4°C, after which cells are washed once in perm/wash solution and once in FACS buffer prior to analysis on a flow cytometer.

5.6 Treatment plan

5.6.1 Stereotactic body radiotherapy (SBRT)

SBRT delivery will be performed using techniques that are in accordance with the 2017 guidelines of European Society for Radiotherapy and Oncology (ESTRO)-ACROP. An intensity-modulated radiotherapy technique will be used to deliver a risk-adapted protocol, with the dose and number of fractions dependent on the size and location of the tumor (72, 73). Standard SBRT doses will be used in accordance with the previous ROSEL study in operable patients [reference]

5.6.1.1 Immobilization, Imaging and Registration

Patients will be set-up using reproducible positioning, verified using an on-line protocol. Immobilization may include a custom immobilization device, such as a vac-loc bag. All patients treated on a linear accelerator will undergo 4-D planning CT simulation as described previously (72). A 4-D planning scan will not be mandatory in patients who undergo MR-guided SBRT [reference].

5.6.1.2 Volume Definitions and Prescription

The gross tumor volume (GTV) will be defined as the visible tumor on CT or MR-imaging (after verification on planning CT). Planning Target Volume (PTV) will be generated in accordance with ESTRO-ACROP guidelines, and the margins used will depend on the choice of imaging and delivery techniques used. All relevant organs at risk in the proximity of the PTV will be contoured. Dose fractionation schemes to be used are listed in Table 2.

Table 2. Dose fractionation schemes according to tumor location

Tumor Size and Location	Total Dose (Gy)	Number of fractions	Dose per fraction (Gy)	Frequency
Tumors 3 cm or less surrounded by lung	54	3	18	Every second day

parenchyma				
Abutting chest wall or >3 cm	55	5	11	Every second day

Organ-at-risk constraints will be those used in the protocol for a phase III trial in patients who were fit to undergo surgery (74). Doses are prescribed to the 80% isodose line encompassing the PTV, resulting in a hotspot of 120-140% in the ITV. 95% of the PTV should be encompassed by the prescription dose, and 99% of the PTV should be covered by 90% of the prescription dose.

5.6.1.3 Quality Assurance

In order to ensure patient safety and effective treatment delivery, a robust quality assurance protocol is incorporated. The following requirements must be completed for each patient:

- Prior to treatment, each patient must be discussed at departmental quality assurance (QA) rounds.
- All radiotherapy plans must meet protocol dose criteria for organs at risk and plans must be approved by physics and verified by the treating physician. Dose constraints should not be exceeded without prior discussion with the responsible radiation oncologist in the study team.
- Institutional treatment verification procedures may vary based upon equipment available, but compliance with ESTRO-ACROP guidelines must be ensured. On linear accelerators cone-beam CT will generally be used to verify tumor localization prior to treatment, and, if indicated, verification can also be performed during and/or after treatment. For MR-guided adaptive SBRT, real-time imaging using gated delivery can be performed.

5.6.2 Pembrolizumab Treatment

Patients randomized to the pembrolizumab arm will be treated with 200 mg pembrolizumab Q3W for 2 cycles or until unacceptable side effects, starting on the first day of radiotherapy.

5.6.2.1 Dose Modification

Pembrolizumab will be withheld for drug-related Grade 4 hematologic toxicities, non-hematological toxicity ≥ Grade 3 including laboratory abnormalities, and severe or life-threatening AEs as per Table 3 below.

Table 3: Dose modification guidelines for drug-related adverse events.

Toxicity	Hold Treatment For Grade	Timing for Restarting Treatment	Treatment Discontinuation
Diarrhea/Colitis	2-3	Toxicity resolves to Grade 0-1	Toxicity does not resolve within 12 weeks of last dose or inability to reduce corticosteroid to 10 mg or less of prednisone or equivalent per day within 12 weeks
	4	Permanently discontinue	Permanently discontinue
AST, ALT, or Increased Bilirubin	2	Toxicity resolves to Grade 0-1	Toxicity does not resolve within 12 weeks of last dose
	3-4	Permanently discontinue (see exception below) ^a	Permanently discontinue

Toxicity	Hold Treatment For Grade	Timing for Restarting Treatment	Treatment Discontinuation
Type 1 diabetes mellitus (if new onset) or Hyperglycemia	T1DM or 3-4	Hold pembrolizumab for new onset Type 1 diabetes mellitus or Grade 3-4 hyperglycemia associated with evidence of beta cell failure	Resume pembrolizumab when patients are clinically and metabolically stable
Hypophysitis	2-4	Toxicity resolves to Grade 0-1. Therapy with pembrolizumab can be continued while endocrine replacement therapy is instituted	Toxicity does not resolve within 12 weeks of last dose or inability to reduce corticosteroid to 10 mg or less of prednisone or equivalent per day within 12 weeks
Hyperthyroidism	3	Toxicity resolves to Grade 0-1	Toxicity does not resolve within 12 weeks of last dose or inability to reduce corticosteroid to 10 mg or less of prednisone or equivalent per day within 12 weeks
	4	Permanently discontinue	Permanently discontinue
Hypothyroidism		Therapy with pembrolizumab can be continued while thyroid replacement therapy is instituted	Therapy with pembrolizumab can be continued while thyroid replacement therapy is instituted
Infusion Reaction	2 ^b	Toxicity resolves to Grade 0-1	Permanently discontinue if toxicity develops despite adequate premedication
	3-4	Permanently discontinue	Permanently discontinue
Pneumonitis	2	Toxicity resolves to Grade 0-1	Toxicity does not resolve within 12 weeks of last dose or inability to reduce corticosteroid to 10 mg or less of prednisone or equivalent per day within 12 weeks
	3-4	Permanently discontinue	Permanently discontinue
Renal Failure or Nephritis	2	Toxicity resolves to Grade 0-1	Toxicity does not resolve within 12 weeks of last dose or inability to reduce corticosteroid to 10 mg or less of prednisone or equivalent per day within 12 weeks
	3-4	Permanently discontinue	Permanently discontinue
All Other Drug-Related Toxicity ^c	3 or Severe	Toxicity resolves to Grade 0-1	Toxicity does not resolve within 12 weeks of last dose or inability to reduce corticosteroid to 10 mg or less of prednisone or equivalent per day within 12 weeks
	4	Permanently discontinue	Permanently discontinue

Note: Permanently discontinue for any severe or Grade 3 drug-related AE that recurs or any life-threatening event.

^a For patients with liver metastasis who begin treatment with Grade 2 AST or ALT, if AST or ALT increases by greater than or equal to 50% relative to baseline and lasts for at least 1 week then patients should be discontinued.

^b If symptoms resolve within one hour of stopping drug infusion, the infusion may be restarted at 50% of the original infusion rate (e.g., from 100 mL/hr to 50 mL/hr). Otherwise dosing will be held until symptoms resolve and the subject should be premedicated for the next scheduled dose; Refer to Table 2 – Infusion Treatment Guidelines for further management details.

^c Patients with intolerable or persistent Grade 2 drug-related AE may hold study medication at physician discretion. Permanently discontinue study drug for persistent Grade 2 adverse reactions for which treatment with study drug has been held, that do not recover to Grade 0-1 within 12 weeks of the last dose.

In case toxicity does not resolve to Grade 0-1 within 12 weeks after last infusion, trial treatment should be discontinued. Subjects with a laboratory adverse event still at Grade 2 after 12 weeks may continue treatment in the trial only if asymptomatic and controlled. For information on the management of adverse events, see Section 5.7.1.

Subjects who experience a recurrence of the same severe or life-threatening event at the same grade or greater with re-challenge of pembrolizumab should be discontinued from trial treatment.

5.6.2.2 Timing of Dose Administration

Trial treatment should be administered on Day 1 of each cycle after all procedures/assessments have been completed as detailed on the Trial Flow Chart (Section 6.0). Trial treatment may be administered up to 3 days before or after the scheduled Day 1 of

each cycle due to administrative reasons. All trial treatments will be administered on an outpatient basis.

Pembrolizumab will be administered as a 30 minute IV infusion (treatment cycle intervals may be increased due to toxicity as described in Section 5.8.1.2). Effort must be made to target infusion timing to be as close to 30 minutes as possible. However, a window of -5 minutes and +10 minutes is permitted (i.e., infusion time is 30 minutes: -5 min/+10 min).

5.6.3 Surgical resection

Surgery will occur 8-10 weeks following SBRT +/- pembrolizumab treatment. Surgery will consist of a lobectomy and may employ either an open approach or a video-assisted thoracoscopic approach. Surgical sampling of ipsilateral hilar and mediastinal lymph nodes at the time of resection is mandatory.

5.7 Concomitant Medications/Vaccinations (allowed & prohibited)

Medications or vaccinations specifically prohibited in the exclusion criteria are not allowed during the ongoing trial. If there is a clinical indication for one of these or other medications or vaccinations specifically prohibited during the trial, discontinuation from trial therapy or vaccination may be required. The final decision on any supportive therapy or vaccination rests with the investigator and/or the subject's primary physician.

5.7.1 Acceptable Concomitant Medications

All treatments that the investigator considers necessary for a subject's welfare may be administered at the discretion of the investigator in keeping with the community standards of medical care.

5.7.2 Prohibited Concomitant Medications

Subjects are prohibited from receiving the following therapies during the Screening and Treatment Phase of this trial:

- Anti-cancer systemic chemotherapy or biological therapy
- Immunotherapy not specified in this protocol
- Investigational agents other than pembrolizumab
- Live vaccines within 30 days prior to the first dose of trial treatment and while participating in the trial. Examples of live vaccines include, but are not limited to, the following: measles, mumps, rubella, chicken pox, yellow fever, rabies, BCG, and typhoid (oral) vaccine. Seasonal influenza vaccines for injection are generally killed virus vaccines and are allowed; however intranasal influenza vaccines (e.g. Flu-Mist®) are live attenuated vaccines, and are not allowed.
- Glucocorticoids for any purpose other than to modulate symptoms from an event of clinical interest of suspected immunologic etiology. The use of physiologic doses of corticosteroids is allowed.

Subjects who, in the assessment by the investigator, require the use of any of the aforementioned treatments for clinical management should be removed from the trial. Subjects may receive other medications that the investigator deems to be medically necessary. The Exclusion Criteria describe other medications which are prohibited in this trial. There are no prohibited therapies during the Post-Treatment Follow-up Phase.

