5.4 On-treatment imaging

The diagnostic CT chest will be repeated within two weeks before surgical resection.

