5.8 Rescue Medications & Supportive Care

5.8.1 Supportive Care Guidelines

Subjects should receive appropriate supportive care measures as deemed necessary by the treating investigator. Suggested supportive care measures for the management of adverse events with potential immunologic etiology are outlined below. Where appropriate, these guidelines include the use of oral or intravenous treatment with corticosteroids as well as additional anti-inflammatory agents if symptoms do not improve with administration of corticosteroids. Note that several courses of steroid tapering may be necessary as symptoms may worsen when the steroid dose is decreased. For each disorder, attempts should be made to rule out other causes such as metastatic disease or bacterial or viral infection, which might require additional supportive care. The treatment guidelines are intended to be applied when the investigator determines the events to be related to pembrolizumab.

Note: if after the evaluation the event is determined not to be related, the investigator does not need to follow the treatment guidance (as outlined below). Refer to Section 5.2.1 for dose modification.

It may be necessary to perform conditional procedures such as bronchoscopy, endoscopy, or skin photography as part of evaluation of the event.

- **Pneumonitis:**
 - For **Grade 2 events**, treat with systemic corticosteroids. When symptoms improve to Grade 1 or less, steroid taper should be started and continued over no less than 4 weeks.
 - For **Grade 3-4 events**, immediately treat with intravenous steroids. Administer additional anti-inflammatory measures, as needed.
 - Add prophylactic antibiotics for opportunistic infections in the case of prolonged steroid administration.
- **Diarrhea/Colitis:**

Subjects should be carefully monitored for signs and symptoms of enterocolitis (such as diarrhea, abdominal pain, blood or mucus in stool, with or without fever) and of bowel perforation (such as peritoneal signs and ileus).

 - All subjects who experience diarrhea/colitis should be advised to drink liberal quantities of clear fluids. If sufficient oral fluid intake is not feasible, fluid and electrolytes should be substituted via IV infusion. For Grade 2 or higher diarrhea, consider GI consultation and endoscopy to confirm or rule out colitis.
 - For **Grade 2 diarrhea/colitis**, administer oral corticosteroids.

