5.10 Subject Withdrawal/Discontinuation Criteria

Subjects may withdraw consent at any time for any reason or be dropped from the trial at the discretion of the investigator should any untoward effect occur. In addition, a subject may be withdrawn by the investigator or the PI if enrollment into the trial is inappropriate, the trial plan is violated, or for administrative and/or other safety reasons. Specific details regarding discontinuation or withdrawal are provided in Section 7.1.3.

A subject must be discontinued from the trial for any of the following reasons:

- The subject or legal representative (such as a parent or legal guardian) withdraws consent.
- Confirmed radiographic disease progression
- Unacceptable adverse experiences
- Intercurrent illness that prevents further administration of treatment
- Investigator's decision to withdraw the subject
- The subject has a confirmed positive serum pregnancy test
- Noncompliance with trial treatment or procedure requirements
- The subject is lost to follow-up
- Administrative reasons

The End of Treatment and Follow-up visit procedures are listed in Section 6 (Trial Flow Chart) and Section 7.1.4 (Visit Requirements). After the end of treatment, each subject will be followed for 30 days for adverse event monitoring. Subjects who discontinue for reasons other than progressive disease will have post-treatment follow-up for disease status until disease progression, initiating a non-study cancer treatment, withdrawing consent or becoming lost to follow-up.

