7.1.2 Clinical Procedures/Assessments

7.1.2.1 Adverse Event (AE) Monitoring

The investigator or qualified designee will assess each subject to evaluate for potential new or worsening AEs as specified in the Trial Flow Chart and more frequently if clinically indicated. Adverse experiences will be graded and recorded throughout the study according to NCI CTCAE Version 4.0. Toxicities will be characterized in terms regarding seriousness, causality, toxicity grading, and action taken with regard to trial treatment.

All AEs of unknown etiology associated with pembrolizumab exposure should be evaluated to determine if it is possibly an event of clinical interest (ECI) of a potentially immunologic etiology (irAE). See Section 5.8.1 regarding the identification, evaluation and management of AEs of a potential immunological etiology.

Detailed information regarding the assessment and recording of AEs can be found in section 7.2.

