7.1.3 Withdrawal/Discontinuation

When a subject discontinues/withdraws prior to trial completion, all applicable activities scheduled for the final trial visit should be performed at the time of discontinuation. Any adverse events which are present at the time of discontinuation/withdrawal should be followed in accordance with the safety requirements outlined in Section 7.2 - Assessing and Recording Adverse Events.

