7.2.3.3 Events of Clinical Interest

Selected non-serious and serious adverse events are also known as Events of Clinical Interest (ECI) and must be reported within 24 hours to the PI and within 2 working days to Merck Global Safety. (Attn: Worldwide Product Safety; [contact])

For the time period beginning when the consent form is signed until treatment allocation/randomization, any ECI, or follow up to an ECI, that occurs to any subject must be reported within 24 hours to the PI and within 2 working days to Merck Global Safety if it causes the subject to be excluded from the trial, or is the result of a protocol-specified intervention, including but not limited to washout or discontinuation of usual therapy, diet, placebo treatment or a procedure.

For the time period beginning at treatment allocation/randomization through 90 days following cessation of treatment, or 30 days following cessation of treatment if the subject initiates new anticancer therapy, whichever is earlier, any ECI, or follow up to an ECI, whether or not related to pembrolizumab, must be reported within 24 hours to the PI and within 24 hours to Merck Global Safety.

Events of clinical interest for this trial include:

1. an overdose of pembrolizumab, as defined in Section 7.2.1 - Definition of an Overdose for This Protocol and Reporting of Overdose, that is not associated with clinical symptoms or abnormal laboratory results.
2. an elevated AST or ALT lab value that is greater than or equal to 3X the upper limit of normal and an elevated total bilirubin lab value that is greater than or equal to 2X the upper limit of normal and, at the same time, an alkaline phosphatase lab value that is less than 2X the upper limit of normal, as determined by way of protocol-specified laboratory testing or unscheduled laboratory testing.*

*Note: These criteria are based upon available regulatory guidance documents. The purpose of the criteria is to specify a threshold of abnormal hepatic tests that may require an additional evaluation for an underlying etiology.

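### Section 5.7.2 takes patients who need glucocorticoids for a non-immunologic reason out of the trial, so steroid-treated radiation pneumonitis can cost the exploratory lung comparisons their pre-surgery CT and resected lobe

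*Combined protocol and SAP*

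**What the plan says.** Section 5.7.2 lists therapies prohibited during the Screening and Treatment Phase. One entry is "Glucocorticoids for any purpose other than to modulate symptoms from an event of clinical interest of suspected immunologic etiology"; physiologic doses are allowed. The consequence is stated for the whole list: subjects who, in the investigator's assessment, "require the use of any of the aforementioned treatments for clinical management should be removed from the trial".

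The surrounding text on steroids and immune events:

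- Section 7.1.2.1: "All AEs of unknown etiology associated with pembrolizumab exposure should be evaluated to determine if it is possibly an event of clinical interest".
- Section 5.8.1, on the steroid guidance: "The treatment guidelines are intended to be applied when the investigator determines the events to be related to pembrolizumab".
- Section 7.2.3.3, after randomization: "any ECI, or follow up to an ECI, whether or not related to pembrolizumab, must be reported within 24 hours to the PI". Its list of such events names an overdose and a liver-test pattern, not pneumonitis.

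On timing and data after leaving the trial:

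- Section 5.4: "The diagnostic CT chest will be repeated within two weeks before surgical resection". The flow chart in 6.1 puts induction at day 1 to 56 and surgery at day 56 to 70.
- Section 7.1.3: on discontinuation, "all applicable activities scheduled for the final trial visit should be performed at the time of discontinuation". Adverse events present at that time are still followed.
- Section 5.11 replaces subjects who do not undergo the trimodality treatment.

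Section 8 defines no analysis set and no rule for missing data.

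**The concern.** Every patient receives SBRT to the lung, so radiation pneumonitis is a foreseeable reason for systemic steroids. If the investigator attributes it to radiation rather than to an immune event, 5.7.2 points to removal from the trial.

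The resected lobe and the repeat CT supply the between-arm comparisons of fibrosis and infiltrate (8.2.1) and of lung density (8.4). The first of these serves exploratory objective 1. A patient removed for pneumonitis is likely to be one whose lung changed most. Losing that patient is outcome-related missing data, which replacement by a new patient does not repair. With 10 patients per arm, one loss is a tenth of an arm.

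**Working it through.** **Step 1: can removal come before the data?** Surgery falls on day 56 to 70 and the CT within the 14 days before it, so the CT falls between day 42 (56 − 14) and day 70. Removal during induction can precede both. The only data duties after leaving are final-visit activities (7.1.3) and adverse event and disease-status follow-up (5.10). Neither secures the pre-surgery CT or the specimen for analysis.

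**Step 2: inputs for size.** The plan disputes or states no figure here, so there is nothing to reproduce. It gives no rate of steroid-treated radiation pneumonitis before surgery. The following are assumptions:

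- p, the proportion with steroid-treated pneumonitis before surgery: 2% and 10%. The first is close to the 1.8% pneumonitis that 4.1.7 reports for pembrolizumab in NSCLC, which is not an SBRT rate. The second borrows the acceptance limit for grade ≥3 in 8.1 and is not an expected rate.
- d, the shift of the lung measure in affected patients: up to 2 SD (d = 1 halves every bias below).
- a, the share of affected patients who stay in the trial.

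**Step 3: formula.** Take the outcome as N(0,1) in unaffected and N(d,1) in affected lungs. The mean among retained patients is p·a·d / (1 − p(1 − a)). Bias is the observed difference (combination − SBRT only) minus the true difference (p_comb − p_SBRT)·d.

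**Step 4: results with d = 2.**

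| p combination / SBRT only | a combination / SBRT only | Bias (SD) |
|---|---|---|
| 2% / 2% | 1 / 0 | 0.02·2 − 0 = +0.04 |
| 10% / 10% | 1 / 0 | 0.10·2 − 0 = +0.20 |
| 10% / 10% | 1 / 0.5 | 0.20 − 0.10/0.95 = +0.09 |
| equal rates | 1 / 1 or 0 / 0 | 0 |
| 10% / 2% | 1 / 0 | 0.20 − 0 − 0.16 = +0.04 |
| 10% / 2% | 0.5 / 0.5 | 0.10/0.95 − 0.02/0.99 − 0.16 = −0.07 |
| 10% / 2% | 0 / 0 | 0 − 0 − 0.16 = −0.16 |

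The sign depends on attribution in each arm and on the true rates. The last row needs no asymmetry in the rule: when rates differ, removing every affected patient erases the true difference of 0.16 SD.

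**Step 5: against the noise.** With 10 retained per arm and full asymmetry, the combination arm is a mixture with variance 1 + p(1 − p)d².

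- At 10%: 1 + 0.1·0.9·4 = 1.36. SE = √((1.36 + 1)/10) = 0.486. The ratio is 0.20/0.486 = 0.41.
- At 2%: 1 + 0.02·0.98·4 = 1.078. SE = √((1.078 + 1)/10) = 0.456. The ratio is 0.04/0.456 = 0.09.

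A shift of 0.41 SE lowers the coverage of a 95% interval to Φ(1.55) − Φ(−2.37), about 93%.

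**Step 6: how many patients.** The expected number affected in an arm of 10 is 0.2 at 2% and 1 at 10%. The chance of at least one is 1 − 0.98¹⁰ = 18% and 1 − 0.90¹⁰ = 65%.

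SD units suit CT density. For the 0–3 histology scores they are only indicative.

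**The case against.** **The rule is softer than it looks.** Section 5.7.2 says should, and leaves the judgement to the investigator. Section 5.7 says only that stopping trial therapy may be required, 5.7.1 permits whatever the patient's welfare needs, and the mandatory list in 5.10 does not name steroid use. This lowers the chance of removal. It does not cancel the specific removal sentence, and it secures no data.

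**The lobe may exist anyway.** Lobectomy is standard of care for these patients, so it would probably go ahead. That stands: loss of the specimen is possible, not certain. The plan still does not say that a removed patient's specimen or CT is collected and analysed.

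**Other routes overlap.** Patients with grade ≥3 pneumonitis may leave under 5.10 for "Unacceptable adverse experiences" or be unfit for surgery whatever 5.7.2 says. That also stands: the 10% scenario credits every removal to 5.7.2, so its incremental effect is smaller.

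**Steroids disturb the co-primary immune data.** They do, and 5.1.3 excludes recent systemic steroid users at entry. But the exemption for immunologic events already lets steroid-exposed samples in.

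**A stronger reading to avoid.** Because 7.1.2.1 and 5.8.1 frame immune events around pembrolizumab, a reader might infer that the rule removes mainly SBRT-only patients and so biases the comparison in a known direction. The documents do not support this. The exemption names no arm, and 7.2.3.3 covers events whether or not they are related to the drug. Section 5.7.2 does not define the Treatment Phase either. If that phase ended with the last treatment, the prohibition would end earlier in the SBRT-only arm (3 or 5 fractions every second day) than in the combination arm, with its second dose three weeks after the first.

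**Conclusion.** The concern holds in limited form. Section 5.7.2 can remove patients from either arm for steroid-treated pneumonitis judged radiation-induced, before the pre-surgery CT and resection. No provision retains those data. The exploratory comparisons in 8.2.1 and 8.4 can then lose patients because of the outcome compared.

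Direction and any difference between arms are unknown. On the assumed inputs, with equal rates and full asymmetry, the bias is at most about 0.09 SE at 2% and about 0.4 SE at 10%. The protocol calls pneumonitis rare in this setting (4.1.7, 10.3.5), which favours the lower end. These figures rest on assumed rates and shifts, and on reading the Treatment Phase as the flow chart's induction phase.

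A reader might also infer that the safety criterion in 8.1 is compromised. A difference between arms cannot affect it, because it uses combination patients only, and adverse events present at removal are still followed. Removals under 5.10 are outside this point. It is a cheap improvement to consider, not a threat to the primary objectives.

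**What to change.** Leave the prohibition, its exemption and the event list in 7.2.3.3 as they are. Change only the consequence of glucocorticoid use in 5.7.2, with the same wording for both arms:

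- Pembrolizumab is held or stopped according to Table 3.
- The subject stays in the trial for adverse event follow-up, the pre-surgery CT and collection of the resection specimen.
- Steroid start, stop and indication are recorded.

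In section 8, state that these patients are included in the lung-tissue comparison of 8.2.1 and the CT comparison of 8.4. For the co-primary immune data, flag samples taken after steroid start and report results with and without them. A general permission for steroids for toxicity of any cause is not needed.

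The cost is one case report form field, one sensitivity analysis and some additional steroid-exposed samples. The CT and specimen are already scheduled.
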